### 5.5.5.2 Treatment

The following management recommendations are intended as guidelines for the investigator and may be modified based on institutional practices or local standard of care, as appropriate.

Initial care includes supportive measures and the administration of supplemental oxygen. In mild cases, recovery often occurs simply by interrupting the administration of the offending medication. Concomitant medication lists should be reviewed for medications besides study treatment which can cause methemoglobinemia

Further treatment is generally indicated when the methemoglobin level is above 20% or is associated with symptoms.

Intravenous methylene blue is the first-line antidotal agent and works by restoring the oxygen carrying capacity of hemoglobin by reduction of methemoglobin from its oxidized state. It is given as a 1% solution at a dose of 1 to 2 mg/kg. Most participants require only 1 dose, and symptoms should resolve within 1 hour. Methylene blue may confound the interpretation of methemoglobin levels detected by co-oximetry; alternative methods should be used after treatment with methylene blue if methemoglobin level monitoring is required. Methylene blue should be used with caution in participants with concurrent use of serotonergic psychiatric medications, as this could increase the risk of serotonin syndrome.

Exchange transfusion and hyperbaric oxygen treatment are second-line options for participants with severe methemoglobinemia whose condition does not respond to methylene blue or who cannot be treated with methylene blue. Participant transfer should occur when life-threatening methemoglobinemia that is refractory to treatment occurs in a facility that cannot provide the appropriate critical care.

### 5.5.6 Criteria to Resume Treatment

Subjects may resume treatment with study drug when the drug-related AE(s) resolve to Grade  $\leq$  1 or baseline value, with the following exceptions:

- Subjects may resume treatment in the presence of Grade 2 fatigue.
- Subjects who have experienced a Grade 3 drug-related skin AE may resume treatment in the presence of Grade 2 skin toxicity.
- Drug-related pulmonary toxicity, diarrhea, or colitis, must have resolved to baseline before treatment is resumed. Participants with persistent Grade 1 pneumonitis after completion of a steroid taper over at least 1 month may be eligible for retreatment
- Participants with drug-related endocrinopathies adequately controlled with only physiologic hormone replacement may resume treatment after consultation with the Investigator.
  - Adrenal insufficiency requires discontinuation regardless of control with hormone replacement

- For participants with Grade 2 AST, ALT and/or Total Bilirubin abnormalities, dosing may resume when laboratory values return to baseline and management with corticosteroids, if needed, is complete.
- Participants with combined AST/ALT AND total bilirubin values meeting discontinuation parameters should have treatment permanently discontinued.

For participants who have BMS-986205/BMS-986205 held for elevations of methemoglobin, dosing may resume when the methemoglobin levels have decreased to below the institutional ULN and any associated AEs have resolved to Grade  $\leq 1$  or baseline value. Dose modification of BMS-986205 should be considered when resuming after a delay.

Immuno-oncology (I-O) agents are associated with AEs that can differ in severity and duration than AEs caused by other therapeutic classes. Nivolumab and BMS-986205 are considered as immuno-oncology agents in this protocol. Early recognition and management of AEs associated with immuno-oncology agents may mitigate severe toxicity. Management algorithms have been developed to assist investigators in assessing and managing the following groups of AEs:

- Gastrointestinal
- Renal
- Pulmonary (For participants with dyspnea, CBC and methemoglobin should be measured)
- Hepatic
- Endocrinopathy
- Skin
- Neurological (For participants with confusion, methemoglobin should be measured)

The above algorithms are found in the Nivolumab IB.

## 5.6 Definition of Dose-Limiting Toxicity

Dose limiting toxicities are defined as any of the items listed below which occur during the first 6 weeks.

- Any Grade 2 drug-related uveitis or eye pain that does not respond to topical therapy and does not improve to Grade 1 severity within 2 weeks of starting therapy OR requires systemic treatment
- Any Grade 2 drug-related pneumonitis or interstitial lung disease that does not respond to dose delay and systemic steroids in 14 days (radiologic changes may take longer to resolve) or Grade 2 myocarditis of any duration.

- Any Grade 3 or greater nondermatologic, nonhepatic, nonhematologic toxicity will be considered a DLT with the following specific EXCEPTIONS:
  - Grade 3 or Grade 4 electrolyte abnormalities that are not complicated by associated clinical adverse experiences, last less than 48 hours and either resolve spontaneously or respond to conventional medical intervention
  - Grade 3 nausea, vomiting, or diarrhea that lasts less than 48 hours and either resolves spontaneously or responds to conventional medical intervention
  - Isolated Grade 3 elevation of amylase or lipase not associated with clinical or radiographic evidence of pancreatitis
  - Isolated Grade 3 fever not associated with hemodynamic compromise (e.g., hypotension, clinical or laboratory evidence of impaired end-organ perfusion)
  - Grade 3 endocrinopathy that is well-controlled by hormone replacement
  - Grade 3 tumor flare (defined as pain, irritation, or rash that localizes to site of known or suspected tumor)
  - Grade 3 fatigue
  - Grade 3 infusion reaction that returns to Grade 1 in less than 6 hours. Any Grade 4 drug-related adverse event including laboratory abnormalities except Grade 4 leukopenia or neutropenia lasting < 14 days.
- Grade 4 methemoglobin levels  $\geq$  15 % and Grade  $\geq$  3 hemolysis (i.e., requiring transfusion or medical intervention such as steroids)
- Any of the following drug-related hepatic function laboratory abnormalities:
  - AST or ALT  $>10$ x ULN for  $> 2$  weeks
  - AST or ALT  $> 15$  x ULN irrespective of duration
  - T. Bilirubin  $>5$  x ULN irrespective of duration

If subjects cannot receive 75% of intended dose of BMS-986205 for reasons other than toxicity and did not experience a DLT, they will be replaced for DLT assessment. Subjects treated at MTD will be monitored for chronic toxicity for 3 months to determine a recommended Phase 2 dose (RP2D).

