## **2.0 STUDY OBJECTIVES**

### **2.1 Primary Objective**

1. To obtain the safety and tolerability of BMS-986205 in combination with nivolumab in unresectable / metastatic HCC in the first or second line setting using CTCAE V5.0 criteria.
2. To determine efficacy as defined by objective response rate (ORR) of BMS-986205 in combination with nivolumab in unresectable / metastatic HCC in the first or second line setting using RECIST (version 1.1).

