### 3.0 STUDY DESIGN

This is a phase I/II study using a Simon optimal two stage design for efficacy of BMS-986205 in combination with nivolumab as illustrated in the schema. For the phase I portion the primary endpoint is to determine safety profile of BMS-986205 in two dose levels with nivolumab in unresectable HCC using CTCAE V5.0 criteria. For the phase II portion the primary endpoints are safety and toxicity and the objective response rate using the using RECIST criteria. Exploratory endpoints include disease control rate (DCR), duration of response (DOR), ORR using iRECIST, progression free survival (PFS), overall survival (OS), and correlative studies.

For phase I dose escalation, up to two dose levels of BMS-986205 will be evaluated: 50 mg daily and 100mg daily. These two dose levels were selected based on the clinical data described above. We have chosen 50 mg daily as the starting dose level given the existing safety data for this dose and the safe use of this dose in use with other immunotherapy combinations. The dose of BMS-986205 will be escalated to 100 mg daily if 0 of the first 3 patients experience a dose limiting toxicity (DLT) at 50 mg BMS-986205. Three additional patients will be added to receive 50 mg BMS-986205 if 1 of the first 3 patients experiences a DLT. The dose of BMS-986205 will be escalated to 100 mg daily if no more than one of six patients experience a DLT at 50 mg BMS-986205. The expansion phase will be conducted after MTD is reached, which will be defined as no more than one of six patients develops a DLT at 50 mg or 100 mg of BMS-986205 daily with nivolumab. If BMS-986205 50mg daily is not tolerated the study will be halted and modified after discussion with the principal investigator (PI) and BMS. The 6 patients at the maximum tolerated dose in the phase I portion treated at MTD will count towards the 17 patients needed in the phase II expansion cohort. The phase II cohort will be run as a Simon two-stage design to allow for early trial stoppage for futility. We designate an ORR as defined by RECIST criteria of 5% as not worthy of further investigation and of 25% as worthy of further investigation. In the first stage 9 patients will be accrued and at least 1 response must be observed within 6 months of treatment (or longer at PI discretion) to continue the trial (n1=9, r1=0) (see study schema). BMS-986205 will be administered orally daily and nivolumab will be administered intravenously until disease progression.

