### **5.0 DOSAGE AND ADMINISTRATION**

#### **5.1 Study Drug Administration**

BMS-986205 is administered orally once day; dosing will vary 50 mg or 100 mg according to each cohort (see schema). BMS-986205 is recommended to be taken within 30 minutes after a meal. Nivolumab 240 mg is administered intravenously every 14 days (1 cycle = 14 days).

At the end of the study period, Bristol-Myers Squibb Company will not continue to supply study drug to subjects/investigators unless the Sponsor-Investigator chooses to extend their study. The investigator is responsible to ensure that the subject receives appropriate standard of care or other appropriate treatment in the independent medical judgement of the Investigator to treat the condition under study.

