## **5.5 Management of Adverse Events from Immunotherapy**

### **5.5.1 Dose Delay BMS-986205 and Nivolumab**

BMS-986205 and nivolumab administration should be delayed for the following:

- Grade 2 non-skin, drug-related AE, with the exception of fatigue, nausea, vomiting and anemia
- Grade 2 drug-related creatinine, AST, ALT and/or Total Bilirubin abnormalities
- Grade 3 skin, drug-related AE
- Grade 3 drug-related fatigue, nausea, vomiting, and anemia
- Grade 3 drug-related laboratory abnormality, with the following exceptions:
  - Grade 3 lymphopenia or asymptomatic amylase or lipase elevations do not require dose delay
  - Hepatic events should be managed as detailed in Section 5.5.3
- Any AE, laboratory abnormality, or intercurrent illness which, in the judgment of the investigator, warrants delaying the dose of study medication

In addition, **only BMS-986205** should be delayed for the following:

- Methemoglobin  $\geq 15\%$
- Clinically significant elevations in methemoglobin (generally 10% with a normal hemoglobin level) with any associated Grade 3 AE (hypoxia, dyspnea, confusion, etc.) attributable to sustained elevations of methemoglobin and not attributable to another etiology
- QTcF  $> 500$  msec confirmed by at least 1 repeat ECG and at least 60 msec above baseline
- If nivolumab dosing is delayed for reasons other than study drug toxicity (e.g., administrative issues, holidays, etc.), BMS-986205 dosing should continue uninterrupted

If nivolumab dosing is delayed for reasons other than study drug toxicity (e.g., administrative issues, holidays, etc.), BMS-986205 dosing should continue uninterrupted. Participants may continue to receive nivolumab during dose delays of BMS-986205 for elevations of methemoglobin and associated events, as well as QTcF prolongations.

For participants with methemoglobin elevations with associated Grade 3 AEs, if contribution of nivolumab to the associated AE cannot be ruled out (e.g., a participant with dyspnea in whom pneumonitis has not yet been ruled out), nivolumab dosing should be delayed as well. If BMS-986205 dosing is delayed, dose reduction may be necessary.

If dosing is resumed after a delay, BMS-986205 may be resumed as soon as the criteria to resume treatment are met. Nivolumab should be resumed as soon as possible after criteria to resume treatment are met but may be resumed later than BMS-986205 given the differences in each drug's administration.

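### DLT evaluability is tested on BMS-986205 exposure alone, so a patient who misses nivolumab in the window can count as DLT-free for the combination

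*Combined protocol and SAP*

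**What the plan says.** The primary objective in Section 2.1 concerns the "safety and tolerability of BMS-986205 in combination with nivolumab". Section 3.0 defines the MTD on the same footing: "no more than one of six patients develops a DLT at 50 mg or 100 mg of BMS-986205 daily with nivolumab".

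The rule for who counts toward that figure appears in Sections 3.0 and 5.6 in the same words. It applies "If subjects cannot receive 75% of intended dose of BMS-986205 for reasons other than toxicity and did not experience a DLT", and such patients are replaced for DLT assessment. Neither section mentions nivolumab exposure, and the protocol does not define a DLT-evaluable population elsewhere.

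Section 5.5.1 covers nivolumab doses delayed for reasons unrelated to drug toxicity, such as administrative problems or holidays. In that case "BMS-986205 dosing should continue uninterrupted".

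Nivolumab is given every 14 days (Section 5.1). The DLT window is 6 weeks in Section 5.6 and 56 days in Section 3.0.

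**The concern.** Evaluability is defined on one drug and the conclusion is drawn on two. This is the rule as written, not an omission that a reader has to fill. A patient whose nivolumab slips for a scheduling reason continues BMS-986205, passes the 75% test, and is counted as having tolerated a combination that was only partly given.

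With six patients and a limit of one DLT, a single misclassified patient can change the decision. The same count governs escalation from 50 mg to 100 mg. The dose that passes is then carried into the expansion, where the six phase I patients at the MTD form part of the 17.

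**Working it through.** **The plan's own figures.** The documents state no operating characteristic for the 3+3 part. The only stated one is the Simon design in Section 14.2 (ORR 5% vs 25%, one-sided 0.05, 80% power). It reproduces, with exact alpha 0.0466 and power 0.812 for 0/9 then 2/17, but it does not bear on this point.

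**Infusions at stake.** At one infusion per 14 days, a 6-week window holds three (days 1, 15, 29) and a 56-day window holds four (adding day 43). One missed infusion is 33% or 25% of planned nivolumab exposure.

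**Effect on the MTD rule.** Let p be the DLT risk with the full combination and q the risk for one patient who missed nivolumab, the other five being fully exposed. Then

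P(at most 1 of 6) = (1 − q)·F + q·G, where F = (1 − p)^5 + 5p(1 − p)^4 and G = (1 − p)^5.

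Neither p nor q is in the documents; both are assumed.

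- p = 0.40: F = 0.07776 + 0.25920 = 0.33696; G = 0.07776.
  - q = 0.40 (full exposure): 0.6 × 0.33696 + 0.4 × 0.07776 = 0.233
  - q = 0.20 (half the risk): 0.8 × 0.33696 + 0.2 × 0.07776 = 0.285
  - q = 0 (no risk): 0.337
- p = 0.33: F = 0.4675; G = 0.1350.
  - q = 0.33: 0.67 × 0.4675 + 0.33 × 0.1350 = 0.358
  - q = 0.165: 0.835 × 0.4675 + 0.165 × 0.1350 = 0.413
  - q = 0: 0.468

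| True DLT rate | All six exposed | One affected, half risk | One affected, 5–10% risk | One affected, no risk |
|---|---|---|---|---|
| 40% | 0.233 | 0.285 | 0.31–0.32 | 0.337 |
| 33% | 0.358 | 0.413 | 0.43–0.45 | 0.468 |

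With two affected patients at a 40% true rate, a 5–10% residual risk gives 0.41–0.44, and zero risk gives 0.475.

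**Direction.** The shift is toward passing whenever q is below p. The documents make that plausible. Section 1.3.1 describes the combination's safety as close to that of nivolumab alone. The DLT list in Section 5.6 includes immune-type events (pneumonitis, uveitis, myocarditis) and deals with infusion reactions, and nivolumab is the only infused study drug.

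**What other sections already cover.** Section 6.1.4 stops BMS-986205 when nivolumab is permanently discontinued. An early stop for a non-toxicity reason would then usually trigger the existing 75% rule. Delayed or skipped infusions without discontinuation remain uncovered.

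**The case against.** Five arguments weigh against the point.

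1. *Large misses should be rare.* Section 13.2.1 allows ±1 day for nivolumab in cycles 1 to 3 (the study calendar says ±3 days), and Section 5.5.1 speaks of delay, not omission. This limits frequency. But neither window carries any consequence for evaluability when it is missed.

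2. *An affected patient still has DLT risk.* This stands. Such a patient will normally have had at least one infusion and is on BMS-986205. The 5-month contraception period in Section 4.1 (30 days plus about five nivolumab half-lives) implies a half-life near (150 − 30)/5 = 24 days, so exposure persists through much of either window. The zero-risk column is therefore an upper bound, and the half-risk column shows about 5 points for one patient instead of 10 to 11.

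3. *Only BMS-986205 is escalated, so tying evaluability to it is defensible.* That would hold if the MTD were a statement about BMS-986205 alone. Section 3.0 makes it a statement about the combination.

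4. *There are backstops.* Section 17.2 requires a DLT meeting that reviews toxicity and dose adjustments, MTD patients are monitored for 3 months, and Section 14.1 makes a positive conclusion conditional on acceptable safety. None of these sets an evaluability criterion, and the last has no numeric boundary.

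5. *The response analysis is not affected.* This stands. A reader might infer that it is unclear whether replaced patients stay in the ORR set. The documents do not support that reading. Section 5.6 replaces patients for DLT assessment only, Section 11.5.4 keeps eligible patients in the response analysis even when treatment was incomplete, and Section 14.1 counts those treated at the MTD.

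**Conclusion.** The point holds in conditional form. The replacement rule tests one drug while the MTD is defined for two, and Section 5.5.1 supplies the route by which a patient under-exposed to nivolumab is counted as DLT-free.

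A reader might go further and infer that the MTD decision is biased as planned. The documents do not show that. They give no frequency of missed nivolumab and no DLT rate without it, and if no infusion is missed the bias is zero. If misses occur and lower DLT risk, one affected patient in six raises the chance of passing by about 5 to 10 points at a true rate of 40% (0.233 to 0.29–0.34), and by about 5 to 11 points at 33% (0.358 to 0.41–0.47). The lower figure assumes the patient keeps half the risk and the upper figure none. The gap concerns delayed or skipped infusions; permanent nivolumab discontinuation is largely covered. The change is worth making before the dose decision because it is cheap and specific.

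**What to change.** First reconcile the DLT windows in Sections 3.0 (56 days) and 5.6 (6 weeks). They imply different nivolumab denominators, so no nivolumab threshold can be applied until they agree. Borrowing the plan's own 75%, for example, would mean 3 of 3 infusions in 6 weeks (0.75 × 3 = 2.25, rounded up) but 3 of 4 in 56 days.

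Then, in both sections, define DLT evaluability by a minimum exposure to both agents within the agreed window. The sponsor should set the nivolumab minimum as a number of scheduled infusions. Patients who fall below either minimum for non-toxicity reasons, without a DLT, are replaced for DLT assessment. No change to the ORR set is needed.

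Nivolumab compliance is already documented (Section 5.7), so no new data are required. The cost is a short amendment and an occasional extra phase I patient. Replacement would be more frequent if all three infusions were required under a 6-week window.

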Endpoints:	
Phase I:
 
 
• Safety profile of BMS-986205 in combination with nivolumab in unresectable HCC using CTCAE V5.0 criteria
 
 
Phase II:
 
 
• Safety profile of BMS-986205 in combination with nivolumab in unresectable HCC using CTCAE V5.0 criteria
 
• ORR of BMS-986205 in combination with nivolumab in unresectable HCC using RECIST 1.1 criteria.
 
 
Secondary Endpoints
 
 
• DCR which include CR, PR and SD from the first report of SD or better until progression by RECIST 1.1
 
• DOR defined by the first report of SD or better until progression by RECIST 1.1
 
• ORR using immune RECIST (iRECIST)
 
• PFS defined by date of enrollment until the first date of documented disease progression or death by RECIST 1.1
 
• OS defined by date of enrollment until death from any cause by RECIST 1.1.
 
• Correlation of PD-1/L1 expression (+/-) and IDO1 expression (+/-) at: 1) baseline, 2) on treatment, and 3) progression, with ORR, PFS and OS.
 

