Statistical Considerations	
This is a phase I/II study using a Simon optimal two-stage design for efficacy of BMS-986205 in combination with nivolumab. In the phase I portion, we will treat patients following 3+3 standard design with dose escalation in BMS-986205 along with fixed dose of nivolumab. BMS-986205 dose level 1 will be 50mg and dose level 2 will be 100mg. 3 patients will be treated with BMS-986205 at dose level 1 of 50mg along with fixed dose of nivolumab. If no patient experiences a DLT at dose level 1, we will add 3 patients will be treated at a dose of 100 mg of BMS-986205 with fixed dose of nivolumab. If 1 of 3 patients has a DLT at DL1, we will add 3 patients at a dose of 50 mg. If <math>\leq 1</math> of 6 patients has a DLT at 50mg of BMS-986205, 3 patients will be treated at 100mg. Maximum tolerated dose will be defined as <math>\leq 1</math> of 6 patients at DL1 or DL2 experiencing a DLT. After identifying the MTD, the phase II expansion phase will be initiated with 3 additional patients at the MTD. A maximum total of 17 patients at MTD will be treated on trial including 6 patients treated during phase I portion at MTD. An interim efficacy analysis will be done after 9 patients (including the 6 patients in phase I portion) have been treated. If at least 1 patient out of the 9 initial patients treated at MTD achieves a response, we will accrue 8 more patients at the MTD. If at least 3 of the 17 patients treated at MTD achieve a response, we will deem the treatment worthy of further study, provided the safety profile is acceptable.
 
The Simon optimal two stage design described above provides 80% power to detect the difference between an acceptable response rate of 25% vs. an unacceptable rate of 5% at the 0.05 level (1-sided). The estimated time to accrue 20-23 patients is 18 months, at approximately 1.1 patients per month. The ORR will be estimated as the proportion of participants who experience an objective response, along with its exact 95% confidence

	interval; the disease control rate will be analyzed similarly. DOR, PFS, and OS will be analyzed using Kaplan-Meier methods; medians and 95% confidence intervals will be computed. DLTs, adverse events, serious adverse events, and clinical laboratory values outside normal limits will be listed for each patient and summarized by body system and dose level in frequency tables.
Estimated Accrual Period:	24 months

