## 14.0 STATISTICAL CONSIDERATIONS

### 14.1 Study Design and Overview of Primary and Secondary Endpoints

This is a phase I/II study using a Simon optimal two-stage design for efficacy of BMS-986205 in combination with nivolumab. In the phase I portion, we will treat patients following 3+3 standard design with dose escalation in BMS-986205 along with fixed dose of nivolumab.

BMS-986205 dose level 1 will be 50mg and dose level 2 will be 100mg. 3 patients will be treated with BMS-986205 at dose level 1 of 50mg along with fixed dose of nivolumab. If no patient experiences a DLT at dose level 1, we will add 3 patients will be treated at a dose of 100 mg of BMS-986205 with fixed dose of nivolumab. If 1 of 3 patients has a DLT at DL1, we will add 3 patients at a dose of 50 mg. If  $\leq 1$  of 6 patients has a DLT at 50mg of BMS-986205, 3 patients will be treated at 100 mg. Maximum tolerated dose will be defined as  $\leq 1$  of 6 patients at DL1 or DL2 experiencing a DLT. After identifying the MTD, the phase II expansion phase will be initiated with 3 additional patients at the MTD. A maximum total of 17 patients at MTD will be treated on trial including 6 patients treated during phase I portion at MTD. An interim efficacy analysis will be done after 9 patients (including the 6 patients in phase I portion) have been treated. If at least 1 patient out of the 9 initial patients treated at MTD achieves a response, we will accrue 8 more patients at the MTD. If at least 3 of the 17 patients treated at MTD achieve a response, we will deem the treatment worthy of further study, provided the safety profile is acceptable.

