### 14.4 Evaluation of Safety

DLTs, adverse events, serious adverse events, and clinical laboratory values outside normal limits will be listed for each patient and summarized by body system and dose level in frequency tables.

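### Once the MTD is chosen, no cohort-level toxicity count can hold accrual, although safety is a phase II primary endpoint

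*Combined protocol and SAP*

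**What the plan says.** Section 3.0 makes safety primary in phase II: "For the phase II portion the primary endpoints are safety and toxicity and the objective response rate". The synopsis endpoint list agrees.

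The cohort rules are these:

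- **Phase I (sections 3.0 and 14.1).** The MTD is a dose with at most 1 DLT in 6 patients. There is a stated consequence at the lower dose: "If BMS-986205 50mg daily is not tolerated the study will be halted and modified".
- **Three-month review (sections 3.0 and 5.6).** "Subjects treated at MTD will be monitored for chronic toxicity for 3 months to determine a recommended Phase 2 dose (RP2D". No event type, grade, count or decider is given.
- **Opening stage 2 (section 14.1).** If at least 1 of the first 9 patients at the MTD "achieves a response, we will accrue 8 more patients at the MTD". Toxicity does not enter this rule.
- **Final decision (section 14.1 and synopsis).** With at least 3 responses in 17, "we will deem the treatment worthy of further study, provided the safety profile is acceptable". Acceptable is not defined.
- **Safety analysis (section 14.4).** Events "will be listed for each patient and summarized by body system and dose level in frequency tables".

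Sections 5.5 and 6.1 give numeric delay, reduction and discontinuation limits for each patient, including hepatic limits specific to HCC. Sections 17.1 and 17.2 provide monthly review of related SAEs, a DSMB if one is required, a research monitor who may stop the trial, weekly case discussion, and a DLT meeting before a move to another dose level.

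**The concern.** The phase I rule rejects a dose at 2 DLTs in 6. The phase II rules contain no counterpart. A dose could enter with 1 DLT in 6 and show 3 more in the next 3 patients, making 4 of 9, and the written stage 2 rule would still add 8 patients if one of the nine had responded. The final proviso comes only after 17 patients. Since it has no content, the same result could be called acceptable or not once the responses are known.

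The question is open in this population. Section 1.3.1 reports treatment-related grade 3 or higher events in 10.9% of 303 subjects at 100 mg, but in a study of advanced malignancies generally. The same section starts this trial at 50 mg in order to look for hepatotoxicity in HCC, and section 5.5.3 admits patients with grade 2 AST or ALT.

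**Working it through.** **1. The plan's own figure.** Sections 14.1 and 14.2 give the response design: 9 patients, stop at 0 responses; 17 patients, success at 3 or more; 5% versus 25%. The exact two-stage binomial gives one-sided alpha 0.0466 and power 0.812, so the stated 0.05 and 80% reproduce. No operating characteristic is stated for safety.

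**2. Strength of the phase I screen.** For a dose level taken by itself with true DLT rate p, P(pass) = (1−p)^6 + 6p(1−p)^5.

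| True rate p | P(at most 1 of 6) |
|---|---|
| 10.9% | 0.868 |
| 1/6 | 0.737 |
| 1/3 | 0.351 |
| 40% | 0.233 |

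At 1/3 this is (64 + 192)/729 = 0.351. The exact 95% interval for 1 of 6 runs from 0.4% to 64.1%.

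**3. What follows a pass.** Up to 17 − 6 = 11 more patients are treated at the dose. No written count holds them. The extreme results that trigger nothing are 1 + 3 = 4 of 9 at the interim and 1 + 11 = 12 of 17 at the end.

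**4. An example trigger.** Hold at 3 of the first 9, 4 of 12, 5 of 15 or 6 of 17, counting section 5.6 DLTs in the phase I window. Start from 0 or 1 event in 6, conditional on a pass, and carry the binomial distribution forward block by block. At p = 1/3 the starting weights are 64/256 = 0.25 for no event and 192/256 = 0.75 for one event.

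- By patient 9: 0.25 × 1/27 + 0.75 × 7/27 = 0.204.
- Patients 10–12 add 0.113, patients 13–15 add 0.075 and patients 16–17 add 0.020.
- Total: 0.41.

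The same recursion at the other rates, with success at ORR 25% if every hold became a stop (0.812 × (1 − hold), response and toxicity independent):

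| True rate | P(hold), given a pass | Success at ORR 25% |
|---|---|---|
| 10.9% | 0.02 | 0.812 × 0.978 = 0.79 |
| 1/6 | 0.07 | 0.812 × 0.928 = 0.75 |
| 1/3 | 0.41 | – |
| 40% | 0.58 | – |

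**5. Patients spared.** At 1/3, summing the probability of no earlier hold over patients 7 to 17 gives 8.5 expected further patients instead of 11. Counted from before phase I, that is 0.351 × (11 − 8.5) = 0.88, or about one patient. The figure assumes that stage 2 always opens, so it is an upper value.

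**6. Why not count to three months.** Assume that the hazard halves after week 6. A 6-week rate of 10.9% then becomes 16.7% by day 91, and a rate of 1/6 becomes 25%. A tighter limit of 3 of 9, 4 of 13 or 5 of 17 on that longer window would be crossed with probability 0.18 and 0.41–0.43 respectively. Success at ORR 25% would fall from 0.81 to about 0.67 and 0.46. That version is expensive at rates the 3+3 rule would accept.

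**The case against.** The strongest reply is that patients are already protected. Each phase II patient is under numeric delay and discontinuation limits, related SAEs are reviewed monthly, and the research monitor can stop the trial. This stands against any inference that the plan has no toxicity limits or that nobody could intervene. It does not supply the missing rule: the limits in sections 5.5 and 6.1 act on one patient at a time, the oversight in section 17 has no stated count, and the DLT meeting in section 17.2 governs a change of dose level, not the opening of stage 2. The cancer center's monitoring plan, cited in section 17.1, is not among the documents, so it cannot be said that this plan contains no limit either.

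A reader might also infer that the safety endpoint is a test that cannot fail. The documents do not support that. They ask for a safety profile, plan tables, and claim no safety hypothesis. What lacks content is the decision proviso and the accrual rule.

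Finally, any numeric limit is a choice. That stands. No tolerable rate is stated, and reasonable boundaries run as loose as 5 of 9 and 9 of 17. The 10.9% is also a different event from a section 5.6 DLT, which exempts several grade 3 events and includes some grade 2 ones. It serves here only as a low reference rate.

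**Conclusion.** The point holds at cohort level. After MTD selection no written toxicity count holds accrual, gives the three-month review a criterion, or defines an acceptable safety profile. It should be corrected, but it is not critical, because patient-level limits and discretionary stopping authority are in place.

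The size is modest. A dose with a true DLT rate of 1/3 reaches phase II with probability 0.35, and the example trigger would then hold it with probability 0.41.

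This rests on the following assumptions: 1/6 as tolerable and 1/3 as not, both read from the 3+3 rule; the same DLT rate before and after the MTD is chosen; each DLT outcome known before the next entry; and independence of response and toxicity for the success figures.

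**What to change.** In sections 14.1, 14.4 and 3.0 and in the synopsis, add one hold-for-review trigger covering all patients treated at the MTD in both phases.

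- **Event:** a DLT exactly as section 5.6 defines it, over the same window as phase I. Section 5.6 says 6 weeks and section 3.0 says 56 days, so one of them must be chosen.
- **Trigger, as an example:** hold accrual at 3 of the first 9, 4 of 12, 5 of 15 or 6 of 17. The sponsor should set the final numbers and state the tolerable rate behind them.
- **Decider:** the existing Data and Safety Monitoring Committee reviews the hold and advises whether to resume, change or stop.
- **Final decision:** require that the trigger has not been crossed before the safety profile is called acceptable.
- **Three-month review:** send later events to the same committee for the RP2D decision, without counting them toward the trigger.

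The cost is a paragraph and matching lines. It adds no patients and leaves the response boundaries unchanged. A hold pauses accrual for the review, with probability 0.02 at a true rate of 10.9% and 0.07 at 1/6, given a phase I pass.
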